3.3.3 Endpoint Definitions

- Duration of viral shedding as assessed by PCR is defined as time to reduction of qPCR to below limit of detection, at the first of two successive measurements.
- Development of resistance is defined as the percentage of subjects who develop a resistant strain population by day 7, as measured by RNA sequencing of NA for recognized oseltamivir resistance mutations (e.g., H275Y or N295S in N1, R292K or E119V in N2).
- Duration of clinical symptoms is defined as the time to alleviation of all clinical symptoms to 0 (absent) or 1(mild) on two successive measurements in absence of symptom relief medications.
- Absence of fever (temperature <38.0°C/100.4°F) for 24 hours without antipyretic.
- Time to resumption of normal activity is defined as time to the time to the first “yes” answer to the global assessment question “Are you functioning as well as you were before you had the flu?” (Section 7.3.1.4).

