4.3 Inclusion Criteria for Enrollment (Screening)

1. Signed informed consent prior to initiation of any study procedures
2. Age ≥ 18 and < 65 years of age
3. One or more respiratory symptoms (cough, sore throat, or nasal symptoms)
4. Onset of respiratory symptoms no more than 48 hours before enrollment (screening)
5. Willingness to have samples stored

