#### **4.9 Secondary Endpoints: Clinical Endpoints [DIARY1] (PEP and ITT)**

Many of the clinical endpoints rely on data collected on diary cards completed by the study participants. The subjects are asked to complete these twice a day (at 8AM and 8PM) on Days 0 through 14 and then again on Day 28. Fever is recorded for the preceding 12 hour period at both times each day, and symptoms are recorded at both times for Days 0 to 7 and then once daily on Days 8 to 14. Functional status (based on the Physical Function domain questions from the SF-36) and two questions giving a global assessment of status are completed daily at 8AM.

- a. Duration of clinical symptoms. Duration of clinical symptoms is defined as the time from Day 0 to the first of two successive measurements at which all clinical symptoms are grade 0 (absent) or 1 (mild). A measurement is considered to be the 8AM or 8PM assessment during Days 0 to 7 (so two measurements are obtained per day) and then the daily assessment thereafter. Time will then be calculated in half-days through to Day 7. For the purposes of defining the endpoint, if the subjects' first two assessments on (baseline assessment and first subsequent diary card assessment) satisfy this criterion, then the duration will be set to zero. Missing values will be ignored [this is equivalent to assuming that a missing value would have (a) indicated at least one grade 2+ symptom if the preceding record includes a grade 2+ symptom or if the first Day 0 value is missing; (b) indicated no grade 2+ symptoms if the preceding and succeeding assessments show no grade 2+ symptoms; and (c) indicated a grade 2+ symptom if the preceding assessment shows no grade 2+ symptom and the succeeding value shows a grade 2+ symptom]. Times will be considered as discrete (i.e. based on the schedule of completion of diary cards) and subjects not having two succeeding assessments with only grade 0 or 1 symptoms at any time during follow-up will be censored immediately after Day 14 (the last scheduled measurement time on which an endpoint can occur).
- Kaplan-Meier plot (and associated table) of the percent of subjects without clinical symptoms per the above definition over time, with the median duration of time to alleviation of such symptoms and its 95% confidence interval.
  - P-value comparing randomized arms from the log rank test.

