  - Sensitivity analyses assuming (a) that missing values would include grade 2+ symptoms, (b) that missing values would not include grade 2+ symptoms, (c) that missing values would include grade 2+ symptoms in one randomized arm and would not include grade 2+ symptoms in the other arm (so as to maximize the difference between arms), and (d) the opposite of (c) (so as to minimize the difference between arms).

Note: Secondary analyses restricting to those with at least one grade 2 (moderate) or grade 3 (severe) clinical symptom based on the Diary Card at randomization, will be conducted for section a described above.

- b. Absence of fever Time to the absence of fever is defined as the time from Day 0 to the first of two successive assessments (through to Day 7) or the first assessment (Day 8 to Day 28) at which no fever  $\geq 38.0^{\circ}\text{C}$  is reported during the prior 12 hours and no antipyretics have been taken during the 24 hours. Time will then be calculated in half-days through to Day 7. For the purposes of defining the endpoint, if the first two assessments on Day 0 or 1 satisfy this criterion, then the duration will be set to zero. Missing values will be ignored [this is equivalent to assuming that a missing value would have (a) indicated fever if the preceding record includes fever or if the first Day 0 value is missing; (b) indicated no fever

if the preceding and succeeding assessments show no fever; and (c) indicated fever if the preceding assessment shows no fever and the succeeding value shows fever]. Times will be considered as discrete (i.e. based on the schedule of completion of diary cards) and subjects not having a 24-hour period without fever at any time during follow-up will be censored immediately after Day 14 (the last scheduled measurement time on which an endpoint can occur).

- Analysis for duration of fever will follow the same approach as for duration of clinical symptoms.
- c. Resolution of Symptoms and Fever. Time to resolution of all symptoms AND Fever is defined as the time from Day 0 to the first of two successive measurements at which all clinical symptoms are grade 0 (absent) or 1 (mild) and no fever  $\geq 38.0^{\circ}\text{C}$  is reported during the prior 12 hours and no antipyretics have been taken during the 24 hours.
- Analysis for duration of clinical symptoms and fever will follow the same approach as for duration of clinical symptoms.

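### Time to absence of fever counts subjects who already meet the criterion as events at time zero, and the SAP plans no baseline-restricted analysis for this endpoint

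*SAP*

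**What the plan says.** Protocol 4.3 asks for "One or more respiratory symptoms (cough, sore throat, or nasal symptoms" among its entry criteria; fever is not one of them. Protocol 3.3.3 defines absence of fever as a temperature below 38.0 °C "for 24 hours without antipyretic", with no restriction to subjects who are febrile at baseline.

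SAP 4.9 item b turns this into a time-to-event endpoint. Through Day 7 the event needs two successive assessments with no fever of 38.0 °C or above in the prior 12 hours and with the condition that "no antipyretics have been taken during the 24 hours". For subjects who qualify at once, "if the first two assessments on Day 0 or 1 satisfy this criterion, then the duration will be set to zero".

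The analysis is carried over from symptom duration: "Analysis for duration of fever will follow the same approach as for duration of clinical symptoms". That means a Kaplan-Meier "median duration of time to alleviation of such symptoms and its 95% confidence interval" and a "P-value comparing randomized arms from the log rank test", in both the Primary Efficacy and ITT populations.

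For symptom duration, the Note under item a adds secondary analyses in subjects with at least one moderate or severe symptom at randomization; these "will be conducted for section a described above". For virology, SAP 4.8.2 item d repeats the analyses in subjects with detectable virus at Day 0. Baseline fever is tabulated (SAP 4.3.3 item i) but is not used to define any analysis set for item b.

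Item b also lets the event occur at a single assessment from Day 8 through Day 28, yet censors subjects without the event just after Day 14 and describes Day 14 as the last scheduled time at which the endpoint can occur.

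**The concern.** A subject with no fever and no antipyretic at the first two assessments has no fever to resolve. Counting that subject as an event at time zero adds a block of tied events, split between the arms essentially by randomization. The block increases the variance of the log-rank statistic but adds almost nothing to its expected value, so a real effect on fever resolution is harder to detect. If the block is large enough, the reported median is zero in both arms and says nothing about how long fever lasted.

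The SAP handles the same problem for symptom duration and for virology by adding a run restricted to subjects who had the condition at baseline. Fever, a listed secondary endpoint, has no such run.

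**Working it through.** **No planned figure to reproduce.** The documents state no power, event count, hazard ratio or expected median for this endpoint.

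**Inputs from the documents.** 560 randomized, 1:1 (SAP Protocol Summary); two-sided 0.05 (Protocol 9.1); half-day grid through Day 7 and the Day 14 censoring rule (SAP 4.9 item b); pilot subjects included in secondary analyses (SAP 4.8). The 560 is an upper bound, because the Primary Efficacy Population is a subset.

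**Assumptions, not in the documents.** Share f at time zero from 0 to 0.7, the same in both arms; hazard ratio for recovery 1.3 or 1.4 among the other subjects; placebo median 2 days among them.

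**Formula.**
- Log-rank variance from subjects not at time zero, ignoring ties: N(1−f)/4.
- Added by the tied block at time zero: about N·f·(1−f)/4, with expected numerator zero.
- After time zero the risk sets are the same with or without the block, so z(all)/z(restricted) = 1/√(1+f).

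Example, f = 0.3 and hazard ratio 1.3:
- Variance: 560×0.7/4 = 98, plus 560×0.3×0.7/4 = 29.4, total 127.4.
- Restricted: √98 × ln 1.3 = 9.90 × 0.2624 = 2.60; power Φ(2.60−1.96) ≈ 74%.
- All subjects: 2.60/√1.3 = 2.28; power Φ(2.28−1.96) ≈ 62–63%.

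**Simulation.** 1,500 trials per setting, N = 560, half-day grid, tied log-rank test with hypergeometric variance. Here, restricted means excluding the time-zero group.

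| f | 1/√(1+f) | z ratio, simulated (HR 1.3) | Power, HR 1.3: all vs restricted | Power, HR 1.4: all vs restricted |
|---|---|---|---|---|
| 0.1 | 0.95 | 0.95 | 80% vs 83% | 93% vs 96% |
| 0.3 | 0.88 | 0.85 | 60% vs 74% | 79% vs 91% |
| 0.5 | 0.82 | 0.77 | 40% vs 59% | 57% vs 78% |
| 0.7 | 0.77 | 0.72 | 22% vs 39% | 36% vs 58% |

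At N = 500 the pattern is the same: at f = 0.3, 54% vs 67% for hazard ratio 1.3 and 78% vs 89% for 1.4.

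**Median.** The Kaplan-Meier median is 0 once survival just after time zero is at or below 0.5, that is f ≥ 0.5. In the simulation it was 0 in no trial at f ≤ 0.4, in about half of trials per arm at f = 0.5, and in every trial at f = 0.6 and 0.7.

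**Which restriction.** Keeping only subjects at 38.0 °C or above is not the same as removing the time-zero group. It also drops subjects whose temperature is lowered by antipyretics and those whose fever starts later; both stay at risk and inform the comparison. Let m be their share of all subjects. With N = 500, hazard ratio 1.4 and f = 0.3, power for the planned analysis versus the temperature-only subset was 76% vs 82% at m = 10%, 77–79% vs 74–76% at m = 20%, and 74–76% vs 64–65% at m = 30% (ranges over two separate simulations at the last two settings). The documents do not give m.

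**Event window.** Diary cards are completed through Day 14 and again on Day 28 (Protocol 7.3.1; SAP 4.9). A subject who first qualifies on Day 28 is an event under the event sentence and censored under the censoring sentence.

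**The case against.** The case for the plan is substantial.

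- **The time-zero group is narrower than it looks.** A reader might infer that everyone afebrile at Day 0 gets a duration of zero. The text does not say so: the subject must also be free of antipyretics and must qualify at the next assessment. Many ill subjects may be taking antipyretics, which lowers f. The second assessment may also follow the first dose, so the group is not purely a baseline group and the absence of treatment signal is an approximation. This stands.
- **The size rests on an unknown.** At f = 0.1 the loss is about 3 points. This stands; the mechanism is certain, its size is not.
- **Replacing the main comparison would go too far.** A reader might infer that the fever comparison should be made in febrile subjects instead. Protocol 3.3.3 has no such restriction, the secondary objectives name the confirmed-influenza and ITT populations, and for symptoms the SAP itself keeps the restricted run secondary. Replacement would change the estimand, and a temperature-only subset can lose power. This stands.
- **Item c is a different case.** Time zero there also requires every symptom to be absent or mild. The calculations do not cover it, so extending the restriction to item c is not supported.
- **The carry-over sentence might bring in the Note.** This does not stand. The Note names section a only, and it selects on symptom grade, so it would not remove subjects without fever.

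**Conclusion.** The gap is real but limited. For any f above zero, the planned log-rank test for time to absence of fever is diluted by about 1/√(1+f), slightly more with half-day ties. Under an assumed hazard ratio of 1.3 to 1.4 and an assumed placebo median of 2 days, the difference in power from an analysis without the time-zero group is about 3 points at f = 0.1, 12 to 14 at f = 0.3 and 19 to 21 at f = 0.5. A reader might infer that the median will be zero; that follows only if about half of an arm meets both conditions at the first two assessments, and the documents give no basis for saying that it will. Nor is there any inflation of type I error. The issue is power and interpretability of one secondary endpoint.

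The mismatch between the Day 28 event window and censoring after Day 14 is a separate inconsistency that needs no assumption.

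**What to change.** In SAP 4.9 item b:

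1. Keep the all-subject analysis as planned.
2. Add a prespecified secondary analysis restricted to subjects who do not meet the absence-of-fever criterion at the pre-dose baseline assessment, that is, temperature at or above 38.0 °C or antipyretic use in the prior 24 hours. Define the subset from pre-dose data only: exclusion based on the first two assessments could depend on treatment. Do not use temperature alone.
3. State how records with duration zero enter the log-rank test. Software that drops them would change the population without notice.
4. Reconcile the event and censoring sentences so that one end day applies to both.

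The cost is a few sentences, written before unblinding, and one further run. Baseline fever is already tabulated, and medication use over the previous 7 days is recorded at screening (Protocol 6.3.1.3). The downside is a smaller set for the supplementary run. It also omits subjects who meet the criterion at baseline and develop fever later, so its gain will fall somewhat short of the simulated figures if there are many of them.

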1 BACKGROUND INFORMATION AND SCIENTIFIC RATIONALE

1.1 Influenza Infections in Humans

1.1.1 Epidemiology

Influenza causes annual epidemics of acute respiratory illness. Most people who get influenza will recover in a few days to less than 2 weeks, but some people will develop complications (such as pneumonia) as a result of influenza, some of which can be life-threatening and result in death. Complications from influenza can happen at any age, but some people are at higher risk of developing serious influenza-related complications. People at higher risk include people 65 years and older, people of any age with certain chronic medical conditions (including asthma, diabetes, immunosuppression, and heart disease), pregnant women, and infants. Despite effective antivirals and vaccines, influenza is responsible on average for 226,000 excess hospitalizations and about 24,000 deaths each year in the United States alone. [1] The number of deaths is estimated to be over 500,000 worldwide.

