9.1 General Considerations

All statistical inferences will be based on two-sided tests with an α -level of 0.05. Categorical data will be summarized by the number and percent of subjects falling within each category. Continuous variables will be summarized by descriptive statistics, including mean, standard deviation, minimum, maximum, median, and relevant percentiles. Time-to-event endpoints will be summarized by median durations, hazard ratios, and corresponding 95% confidence intervals. Study Day 0 will be defined as the day of randomization.

The Statistical Analysis Plan will provide the procedure for accounting for missing, unused, and spurious data.

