### **Secondary Endpoints**

#### Clinical Endpoints:

- Time to alleviation of influenza clinical symptoms
- Time to absence of fever
- Time to resumption of normal activity
  - Note: in this analysis, the following endpoints will be used to represent “resumption of normal activity”:
    - Time to feeling as good as before the onset of the influenza illness (as measured by a global assessment question)
    - Time to return to pre-influenza illness level of function (as measured by a global assessment question)
    - Time to return to pre-influenza illness level of physical function (as measured by SF-36 physical score)
- Number of premature study treatment discontinuations
- Proportion of subjects who develop bronchitis, pneumonia, or other complications of influenza
- Proportion of subjects who require hospitalization
- 28-day mortality

Virologic Endpoints: (assessed by PCR in NP swab)

- Duration of viral shedding
- Change in viral shedding as a function of time
- AUC of viral shedding
- Frequency of emergence of antiviral resistance

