- d. Global assessment: Times to “feeling as good as you did before you had the flu” and “functioning as well as you did before you had the flu” will be defined as the times of two successive measurements with “yes” responses to the respective global assessment questions.
- The details of the definition, handling of missing values and analysis will follow that for duration of clinical symptoms.
- e. Functional status: This is assessed using the 10-item domain of Physical Function from the SF-36, and calculated as the average of the scores of all 10 items. Functional status is evaluated daily through to Day 14 and then at Day 28.
- Scoring, including handling of missing values, will be undertaken per the standard instructions for the RAND 36-Item Health Survey 1.0 instrument (located at: [http://www.rand.org/health/surveys\\_tools/mos/mos\\_core\\_36item\\_scoring.htm](http://www.rand.org/health/surveys_tools/mos/mos_core_36item_scoring.htm) 1). If all 10 components are not scored, the pre-illness functional status will be scored as missing.
  - Figure and associated Table: Median, 25th and 75th percentiles, (and min and max value in table), with sample size, at each required measurement time.
  - Figure and associated Table: Median, 25th and 75th percentiles, (and min and max value in table), with sample size, change from Day 0 at each required measurement time.

- Statistical comparison between randomized arms of changes in score will be undertaken at Days 3, 7, 14 and 28 using Wilcoxon's test.
  - Time to return of physical function to pre-illness level is defined as the time from Day 0 to the first of two successive measurements at which the physical function score equals or is better than the pre-illness score (obtained by recall at enrollment). Time will be calculated in daily increments through to Day 14. For the purposes of defining the endpoint, if a subject's Day 0 and Day 1 assessments satisfy this criterion, then the duration will be set to zero. Missing values will be ignored. Times will be considered as discrete (i.e. based on the schedule of completion of diary cards) and subjects not having two successive assessments with scores equal to or better than the pre-illness score will be censored immediately after Day 14 (the last scheduled measurement time on which an endpoint can occur).

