- g. AUCs will be calculated for the self-collected swabs. This is defined as the area below the line formed by joining the measured values at each successive scheduled measurement time and above the limit of detection. This will be calculated using the trapezoidal rule. Missing values will be ignored (this is equivalent to imputing a missing value using linear interpolation between the previous and succeeding available values). If the Day 0 value is missing, then the subject will be excluded from the analysis.
  - Figure and associated table showing number of subjects and minimum, maximum, median, 25% and 75% percentile of the value of viral shedding at each scheduled measurement time. This will be presented (a) imputing values

as defined above for the calculation of AUC, and (b) using observed values only.

- Table showing number of subjects and minimum, maximum, median, 25% and 75% percentile of the AUC, both over all subjects and by strata defined by quartile of Day 0 measurement.
- P-value comparing randomized arms from Wilcoxon rank sum test stratified by quartile of Day 0 measurement.

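### SAP 4.9e tests change in SF-36 physical function from Day 0 without adjustment; at Days 14 and 28 that change is mostly Day 0 variation, so these supportive tests lose much of their achievable power

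*SAP*

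**What the plan says.** SAP 4.9e describes functional status as "assessed using the 10-item domain of Physical Function from the SF-36, and calculated as the average of the scores of all 10 items". It tabulates the score by arm at each time point, then tabulates "change from Day 0 at each required measurement time". The test follows: "Statistical comparison between randomized arms of changes in score will be undertaken at Days 3, 7, 14 and 28 using Wilcoxon's test". The test bullet does not name the reference day, but change from Day 0 is the only change defined. No test of the score itself is planned, and no stratification or covariate is named. Section 4.9 applies to both the PEP and the ITT population.

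The same item defines a time-to-event outcome: first return to the recalled pre-illness score on two successive assessments, with Kaplan-Meier curves and a log-rank test, censored just after Day 14. That outcome, not the change-score tests, appears in the SAP's list of secondary endpoints.

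Elsewhere the SAP handles a baseline measurement differently. For the AUC of self-collected swabs, 4.10g specifies: "P-value comparing randomized arms from Wilcoxon rank sum test stratified by quartile of Day 0 measurement".

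**The concern.** The physical function score has a hard upper limit, reached when all ten items are answered as not limited (Protocol 7.3.1.3, Table 5). The trial enrolls low-risk adults, and Protocol 1.1.1 states: "Most people who get influenza will recover in a few days to less than 2 weeks". As subjects reach the cap, the follow-up score tends to a constant, and change from Day 0 tends to that constant minus the Day 0 score. Ranking subjects on change then mostly ranks them by how limited they were at enrollment.

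The Day 0 assessment precedes the first dose and randomization balances it on average, so this variation is noise in the arm comparison. The stake is that a real difference in function at Day 14 could be missed by this test, and the null result then read as contradicting a favorable time-to-return result.

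**Working it through.** **What the plan gives.** There is no SF-36 standard deviation (SD), effect size, recovery share or power target in either document. The only figure to reproduce is the trial's size. Protocol Table 9 gives 490 for 42.5% against 57.5%. Exact Fisher power at 245 per arm is 90.3%, and 245/0.9 = 272.2, rounded up to 273 per arm, gives the stated 546. From 510 main-study subjects with 10% missing (stated for Day 3 qPCR, assumed here for the diary), 510 × 0.9 / 2 ≈ 229 per arm. Adding the pilot subjects, whom SAP 4.8 includes in secondary analyses, gives 560 × 0.9 / 2 = 252, which does not change the comparison.

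**Normal theory.** Let s0 and st be the SDs at Day 0 and Day t, and r their correlation.
- Var(change) = s0² + st² − 2·r·s0·st.
- Variance after adjusting for Day 0 = st²(1 − r²).
- Relative efficiency of change = st²(1 − r²) / Var(change).
- Change is less variable than the raw score only if r > s0/(2·st). This fails once st is small.

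Example with s0 = 25, st = 12.5, r = 0.4: Var(change) = 625 + 156.25 − 250 = 531.25; adjusted variance = 156.25 × 0.84 = 131.25; efficiency = 0.247. If the adjusted test had 90% power, the change test would have Φ(√0.247 × (1.960 + 1.282) − 1.960) = Φ(−0.35) ≈ 36%.

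| st/s0 | Efficiency, r 0.2-0.6 | Power of change test where adjusted test has 90% |
|---|---|---|
| 1 (little recovery) | 0.60-0.80 | 71-83% |
| 0.5 | 0.23-0.25 | 34-36% |
| 0.33 | 0.10-0.11 | 18-19% |
| 0.2 | 0.03-0.04 | 8-10% |

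**Simulation A (assumed inputs).** 450 subjects; ten items of three levels rescaled to 0-100 in steps of 5 and capped; Day 0 mean 50; latent normal scores; two-sided 0.05.

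| Visit | Assumptions | Change from Day 0 | Score, stratified by Day 0 quartile |
|---|---|---|---|
| Day 3 | SDs 22-25, r 0.5, shift 6 | 62-79% | 79-89% |
| Day 7 | mean 88, SD 16, shift 5; Day 0 SD 25, r 0.35 | 36% | 89% |
| Day 7 | as above; Day 0 SD 15, r 0.5 | 76% | 93% |
| Day 14 | mean 96, SD 12, shift 4; Day 0 SD 15-25 | 19-42% | 89-94% |

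Repeat runs move these by a few points. Day 0 explained 41-74% of the variance of change at Day 7 and 73-89% at Day 14. With no effect, rejection rates were 5-6%. At Days 3 and 7 the stratified test led by 8 points or more, unless r was as high as 0.8, where the two were about equal.

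**Simulation B (assumed inputs).** 229 per arm; each subject is either recovered to the pre-illness level or not, with the unrecovered share differing by arm. The adjusted test here is a rank analysis of the score given Day 0.

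| Visit | Unrecovered, placebo vs oseltamivir | Change | Score | Adjusted |
|---|---|---|---|---|
| Day 3 | 80% vs 68% | 25-45% | 41-54% | 60-66% |
| Day 7 | 45% vs 31% to 60% vs 45% | 17-60% | 57-74% | 64-85% |
| Day 7 | 20% vs 10%, 30% vs 18% | 10-40% | 28-70% | 29-77% |
| Day 14 | 20% vs 10%, 15% vs 7% | 6-22% | 23-56% | 22-59% |
| Day 28 | 8% vs 2.5%, 6% vs 2% | 4-7% | 8-29% | 9-29% |

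In the five settings run per visit for 15% vs 7% (Day 14) and 6% vs 2% (Day 28), Day 0 explained 71-87% and 80-93% of the variance of change. At Day 3 its correlation with change was −0.37 to −0.66, so it explained 14-44%. The Day 3 loss is larger in this model than in A, but Day 0 does not dominate there.

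**The case against.** The strongest reply is that little depends on these tests. They are not listed endpoints and were never powered. The listed SF-36 endpoint uses the pre-illness reference with a log-rank test, and 4.9d adds two global-assessment time-to-event tests; none of them subtracts Day 0. A reader might infer that a real effect on functional recovery would be reported as no difference. The documents do not support that, because these other tests remain. A reader might also infer bias; there is none, since Day 0 is pre-dose and randomized.

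Three further points stand.
- It would be wrong to say that all four visits are dominated by Day 0 variation. At Day 3 under model A with r 0.5, change and the unadjusted score perform similarly (64-78% against 67-82%), and at r 0.6 change does better. Only adjustment adds power there.
- Day 7 cannot be grouped with the recovered visits. Protocol 1.1.1 supports recovery within two weeks, not by one week.
- Model A is generous to the fix at Day 14. Scores round to 100 when the latent value is at least 97.5, so P(Z > (97.5 − 96)/12) = 45% of placebo and P(Z > (97.5 − 100)/12) = 58% of treated subjects are at the cap. That is hard to square with most people recovering within two weeks. With 80-93% recovered (model B), the adjusted test reaches only 22-59%.

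What does not stand is that the tests are therefore fine as written. They are the only planned tests of how far function differs on a given day, and the time-to-return endpoint is censored just after Day 14, so Day 28 has no other SF-36 test.

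**Conclusion.** The concern holds for efficiency only. At Days 14 and 28 an unadjusted test of change from Day 0 is driven mainly by pre-treatment variation, and in every setting examined it had well under the power of a test of the score. At Day 7 the loss runs from modest (76% against 93%) to severe (36% against 89%), depending on how many have recovered. At Day 3 it is modest under the main assumptions. At Day 28 there may be little for any test to find.

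The direction follows from the cap, the expected recovery and the pre-dose timing of Day 0. The size does not follow from the documents: every SD, correlation, mean and effect above is assumed. Type I error is intact, and the listed time-to-return endpoint is untouched. The change is still worth making because it costs almost nothing.

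**What to change.** In SAP 4.9e, replace the test sentence with one to this effect: at each of Days 3, 7, 14 and 28 the arms are compared on the physical function score at that day by a Wilcoxon rank sum test stratified by quartile of the Day 0 score, with a Hodges-Lehmann estimate of the shift and its 95% confidence interval. Keep the table of change from Day 0 as description only.

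The stratified method is already in 4.10g. The cost is one sentence and a few lines of code, with no new data. Subjects without a Day 0 score drop out of the stratified test, but a change score already loses them. With many scores tied at the cap, the estimated shift may be zero at late visits, so it should be read beside the score percentiles already tabulated.

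Comparing change from the recalled pre-illness score is an alternative. It had more power in model B at Day 14 (52-87%), but that assumes accurate recall and is the optimistic end. Whichever is chosen should be fixed before arm-level results are seen.
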